6.1.2.5 Time to Initiation of a New Antineoplastic Therapy

The start of a new antineoplastic therapy is based on the information collected in the (new) prostate cancer drug therapy CRF pages about all antineoplastic therapies, including cytotoxic and hormone therapies, initiated for prostate cancer subsequent to the study drug.

In patients with a new antineoplastic therapy initiated for prostate cancer after randomization, time to start of a new antineoplastic therapy is defined as the time interval from randomization to the date of first dose administration of the first antineoplastic therapy.

In patients with no new antineoplastic therapy initiated for prostate cancer after randomization, time to start of new antineoplastic therapy will be censored on the last visit date or the date of randomization, whichever occurs last. Patients entering the open-label phase without initiation of a new antineoplastic therapy would be censored on the date entering the open-label phase.

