- ‡ After treatment discontinuation, all subjects MUST undergo long-term follow-up. Long-term follow-up assessments will be composed of post-treatment follow-up and survival follow-up. For those subjects who discontinue study treatment without radiographic disease progression confirmed will undergo post-treatment follow-up (calculated from baseline), include monitoring for survival status, disease progression, new antineoplastic therapies for prostate cancer and symptomatic skeletal events. Subjects will continue to be scanned along with collecting PSA and testosterone every 12 weeks until radiographic progression is confirmed by investigator assessment or the required number of PSA progression events for the final analysis is reached. For those subjects who discontinue study treatment due to confirmed radiographic disease progression will undergo survival follow-up (calculated from date of progression), include monitoring for survival status, new antineoplastic therapies for prostate cancer and symptomatic skeletal events, and the follow-up may be conducted by telephone interview. If seen in clinic, QoL assessment will also be completed until the initiation of new antineoplastic therapy for prostate cancer or the required number of PSA progression events for the final analysis is reached. Additional follow-up contacts may be requested.
- § Or prior to initiation of another investigator agent or new antineoplastic therapy for prostate cancer, whichever occurs first.
- ¶ A brief physical examination is required at each visit, with the exception of the screening visit during which a complete physical examination will be completed.
- †† Laboratory assessments include serum chemistries and hematology.
- ††† For subjects who discontinue study treatment without confirmed radiographic progression, subjects will continue to be collected PSA and testosterone every 12 weeks until radiographic progression is confirmed or the required number of PSA progression events for the final analysis is reached.
- §§ The abdominal-pelvic contrast CT scan or MRI, bone scan, chest x-ray or chest contrast CT must occur within 6 weeks of day 1; otherwise the screening visit assessment must be repeated. Radiographic assessments performed prior to informed consent, as part of the routine care, may be used as the baseline assessment if performed within 6 weeks of day 1 and if digital format images are available for submission to the sponsor.

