### 12.10.2 Schedule and Assessments

For procedures see [Table 4](#) (Open-Label Phase Schedule of Assessments).

After being discontinued from the double-blind period and unblinding, subjects treated with placebo during the double-blind period will sign informed consent at the Open-Label screening visit after which they will be switched to enzalutamide in Open-Label Day 1(dosing below); these subjects will be required to return for study visits at Open-Label Week 5 (Day

- CONFIDENTIAL -

29), Week 13 and every subsequent 12 weeks. Subjects treated with enzalutamide during the double-blind period will sign informed consent at the Open-Label screening visit and will continue receiving enzalutamide during the open-label phase; these subjects will be required to return for study visit every 12 weeks.

During the open-label phase, all subjects will take enzalutamide as four 40-mg soft gelatin capsules (160 mg/day) by mouth once daily with or without food, except that subjects who had a dose modification of enzalutamide during the double-blind period may continue at the current dose as appropriate. Dose modification is allowed during the open-label phase [[Section 5.1.2 Increase or Reduction in Dose of the Study Drug\(s\)](#)].

Study assessments will include safety evaluations including AEs, concomitant medications, clinical laboratory tests, brief physical examinations, ECGs and vital signs. During the open-label phase, for subjects who did not achieve radiographic disease progression, radiographic assessments (CT/MRI and bone scan) are recommended to be performed based on the investigator's discretion and clinical practice, but the data will not be collected in the study.

[figure not shown]
Subjects will have a safety follow-up 30 days after the last dose of open-label enzalutamide. If a new antineoplastic or investigational anticancer treatment is started before 30 days after the last dose of open-label enzalutamide, then safety follow-up should occur immediately before starting the new treatment.

Long-term follow-up data will be collected every 12 weeks. The information collected will include survival status, new antineoplastic therapies for prostate cancer, skeletal-related events and associated interventions.

- CONFIDENTIAL -

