#### **12.10.7 Statistical Methods**

Data collected in the open-label phase will be summarized by descriptive statistics for subjects started open-label enzalutamide in the open-label phase before the study-wide unblinding, and as needed and appropriate for all subjects who received open-label enzalutamide after study-wide unblinding, unless otherwise specified. The details will be provided in the applicable SAPs. The subjects who start open-label enzalutamide before the study-wide unblinding are post-radiographic progression.

Subject disposition data (subjects who continued to the open-label phase and primary reasons for treatment discontinuation and study discontinuation) will be summarized descriptively in the ITT population for subjects who started open-label enzalutamide for the open-label phase, as needed and appropriate.

Safety data will be summarized for subjects receiving open-label enzalutamide as applicable.

Enzalutamide exposure will be summarized and listed in the open-label phase, as needed and appropriate.

Adverse events will be coded using MedDRA. The number and percentage of AEs, SAEs, AEs leading to discontinuation and AEs related to study drug will be summarized by system organ class and preferred term. The number and percentage of AEs by severity (reported according to NCI-CTCAE version 4.03) will also be summarized. All AEs will be listed.

For quantitative laboratory measurements and vital signs, descriptive statistics will be used to summarize results and change from baseline by visit. Baseline will be defined as the latest value recorded prior to the first enzalutamide administration. Using the NCI-CTCAE version 4.03, laboratory values will be classified as Grade 1 through 4, where possible. Laboratory and vital sign data will be displayed in listings.

- CONFIDENTIAL -

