- 7 Adverse events collection begins after the signing of the informed consent for the double-blind period and will be collected until 30 days after the last dose of study drug (including the double-blind period and open-label phase if applicable), or initiation of a new therapy for prostate cancer, or the subject is determined to be a screen failure, whichever occurs first. During the post treatment follow-up period, only symptomatic skeletal events need to be reported.
- 8 Long-term follow-up assessments include survival status, symptomatic skeletal events and new antineoplastic therapies for prostate cancer. May be obtained by telephone contact, chart review or clinic visit.

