3.2 Study Design

This is a multicenter phase 3, randomized, double-blind, placebo-controlled efficacy and safety study of enzalutamide plus ADT versus placebo plus ADT in Chinese subjects with mHSPC, followed by an open-label phase (only for the subjects in placebo arm who discontinue from the study treatment and unblinding of the study treatment assignment are performed after radiographic progression in the judgement of the investigator and in consultation with the medical monitor. This information is necessary to determine the next course of therapy).

Approximately 180 Chinese subjects will be randomized centrally enzalutamide plus ADT or placebo plus ADT (2:1), and the randomization will be stratified by volume of disease (low versus high) and prior docetaxel therapy for prostate cancer (no prior docetaxel, prior docetaxel). High volume of disease is defined as metastases involving the viscera or, in the absence of visceral lesions, there must be 4 or more bone lesions, at least 1 of which must be in a bony structure beyond the vertebral column and pelvic bone. Prior docetaxel therapy is defined as 1 or more cycles of docetaxel but no more than 6 cycles. Re-screening may be allowed once after screening failure upon discussion with the medical monitor.

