Study drug therapy should be continued as long as the subject is tolerating the study drug and continues ADT until radiographic disease progression is documented as outlined in table 3 or starting another investigational agent or new therapy for treatment of prostate cancer. It is recommended that subjects remain on study treatment until confirmed radiographic disease progression. Subjects who discontinue study treatment without confirmed radiographic disease progression will continue to follow the PSA and radiographic assessment schedule until confirmed radiographic disease progression event. In the judgment of the Investigator, for subjects who discontinue study treatment with confirmed PSA progression by central review, blinding suggests to be continued until confirmed radiographic disease progression. In consultation with the medical monitor, unblinding of the study treatment assignment may be performed after radiographic progression if the subject discontinues from the study treatment and in the judgement of the investigator this information is necessary to determine the next course of therapy. Open-label enzalutamide will be supplied for free to the subjects in placebo arm who remain on study treatment until confirmed radiographic disease progression and in the judgement of the investigator who is necessary to initiate the next course of therapy till next disease progression based on the subject's informed consent.

Study films (CT/MRI and bone scan) should be read on site and also be submitted in digital format to the sponsor-designated facility in case independent central review is required after the end of study. Each site should ideally designate the same reader who will evaluate the images for any one subject for the duration of the trial.

Radiographic disease progression is defined by Response Evaluation Criteria in Solid Tumors (RECIST) version 1.1 for soft tissue disease or the appearance of 2 or more new lesions on bone scan. The documentation and confirmation required for the determination of radiographic progression is listed in full protocol [Section 5.3.1.2 CT/MRI and Bone Scan].

The following assessments of prostate cancer status will be collected during the course of the study: PSA, soft tissue disease on CT scan or on MRI, bone disease on radionuclide bone scans, EQ-5D-5L, QLQ-PR25, FACT-P for QoL and BPI-SF for pain symptom assessment.

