Previous, concomitant, and post-treatment medications (both PC and non-PC related for previous and concomitant, and only PC related for post-treatment) reported in the corresponding eCRFs, will be coded with World Health Organization Drug Reference List

(WHO-DD), and will be summarized separately by presenting the number and percentage of subjects by therapeutic subgroup (ATC 2nd level) and chemical subgroup (ATC 4th level) and preferred WHO name. It will be ordered alphabetically by ATC subgroup and decreasing order of frequency of preferred WHO name within each ATC class. Subjects taking the same medication multiple times will be counted once per medication and period.

Previous and concomitant non-medications reported in the corresponding eCRF will be summarized separately by presenting the number and percentage of subjects by reported name. It will be ordered alphabetically and decreasing order of frequency of reported name. Subjects having the same non-medication multiple times will be counted once per non-medication and period.

New antineoplastic prostate cancer therapy are therapies started after the last dose date of study drug, including cytotoxic and hormone therapies. They are recorded as 'antineoplastic medication' in the eCRF (either prostate cancer drug therapy eCRF page, with 'antineoplastic medication' ticked; or on the new prostate cancer drug therapy eCRF page with 'antineoplastic medication' ticked).

All (new) antineoplastic prostate cancer therapies (started on or after first dose of study drug date) will also be summarized separately on the first new antineoplastic prostate cancer after study drug ended. The summary of first new antineoplastic prostate cancer therapy will be provided for the ITT and SAF population.

All previous, concomitant and post-treatment medications or non-medications recorded in the eCRFs will be listed, as well as all new antineoplastic prostate cancer therapies.

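### Time to new antineoplastic therapy is censored at open-label entry, which before study-wide unblinding only progressed placebo patients can reach; define the status of open-label enzalutamide and add supplementary analyses

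*SAP*

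**What the plan says.** - **Censoring rule.** SAP 6.1.2.5: "Patients entering the open-label phase without initiation of a new antineoplastic therapy would be censored on the date entering the open-label phase".
- **Who can enter.** SAP 3.2 describes the open-label phase as "only for the subjects in placebo arm who discontinue from the study treatment" and adds: "Open-label enzalutamide will be supplied for free to the subjects in placebo arm who remain on study treatment until confirmed radiographic disease progression". Protocol 12.10.3 (inclusion criterion 1) sets the same limit for the period before study-wide unblinding. Protocol 12.10.7 confirms the disease state: "The subjects who start open-label enzalutamide before the study-wide unblinding are post-radiographic progression". Protocol 12.10.1 makes entry depend on the investigator judging that a next course of therapy is needed. After study-wide unblinding, Protocol 12.10 opens the phase to both arms.
- **What happens to a progressed enzalutamide patient.** Under the long-term follow-up footnote of Protocol Table 1, patients who stop because of confirmed radiographic progression "will undergo survival follow-up (calculated from date of progression), include monitoring for survival status, new antineoplastic therapies for prostate cancer". Protocol 7.4.2 counts every antineoplastic therapy, hormonal ones included.
- **What counts as new.** SAP 7.2.4: "New antineoplastic prostate cancer therapy are therapies started after the last dose date of study drug, including cytotoxic and hormone therapies". SAP 6.1.2.5 likewise refers to therapy subsequent to the study drug.
- **What is collected after entry.** Footnote 8 of Protocol Table 4: "Long-term follow-up assessments include survival status, symptomatic skeletal events and new antineoplastic therapies for prostate cancer". Protocol 12.10.2: "The information collected will include survival status, new antineoplastic therapies for prostate cancer, skeletal-related events and associated interventions".
- **Status of the endpoint.** It is analysed by the same stratified log-rank and Cox methods as TTPP (SAP 7.4.2.5), but SAP 7.1 makes no multiplicity adjustment for it and says its p-values are descriptive.

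**The concern.** Two patients progress radiographically and each is judged to need further treatment. If the patient was on placebo and takes the open-label option, he leaves the analysis as a censored observation that day. If he was on enzalutamide, he starts another drug and is an event. The censoring happens in one arm only and is triggered by progression, which is what leads to new therapy. Censored placebo patients therefore do not resemble those who stay at risk, and the usual assumption of non-informative censoring is not credible.

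What is at stake is the reading of one of eight secondary endpoints. Its HR and 95% CI will be reported as the effect on time to next therapy, and no sensitivity analysis of it is planned. The SAP also never says outright whether open-label enzalutamide is a new therapy, so a reader cannot tell which quantity the HR estimates.

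**Working it through.** **Plan's own figures.** The documents give no HR, event count or median for this endpoint. The primary design figures reproduce: 75 events, HR 0.5 and 2:1 allocation give 80.8% power at two-sided 0.05, and 60 events at 0.0244 give 61.0%. Neither involves the rule in SAP 6.1.2.5.

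**Step 1: is open-label enzalutamide study drug or new therapy?**

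| Points to study drug | Points to next therapy |
|---|---|
| The adverse event collection rule (Protocol Table 1 footnote, 5.5.1, 5.5.5) includes the open-label phase in its last dose of study drug and makes a new therapy an end of collection; Table 4 nevertheless collects adverse events throughout the open-label phase | Protocol 12.10.1 ties open-label drug to the need for a next course of therapy |
| Protocol 12.10.6 makes starting a new therapy a reason to stop open-label enzalutamide | Protocol 7.4.2 counts all antineoplastic therapies, hormonal ones included |
| SAP 6.2 refers to open-label study drug and lists its start separately from new antineoplastic therapy | |
| SAP 6.1.2.5 speaks of entering open-label without having started a new therapy | |

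The balance favours study drug, but 6.1.2.5 does not say so.

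**Step 2: size if it counts as next therapy.** Let q be the share of first placebo next therapies that are open-label entries. A patient leaves the risk set on the same day whether entry is coded as an event or a censoring, so only the placebo event count changes:

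placebo hazard under the rule = (1-q) × placebo hazard of any next therapy, so HR under the rule = HR/(1-q).

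With an assumed HR of 0.50:
- q = 10%: 0.50/0.90 = 0.56
- q = 25%: 0.50/0.75 = 0.67
- q = 50%: 0.50/0.50 = 1.00, and above 1 for larger q

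Large-sample Cox simulation agreed within 0.3%, both with constant q and in a model allowing open-label entry only after progression (realised q 0.222: ratio 1.286 against 1/(1-0.222) = 1.285).

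Expected placebo events come from n = 60, 15 months of accrual plus 12 of follow-up (Protocol synopsis), and an assumed placebo median of 18 months. With L = ln2/18 = 0.0385:

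60 × [1 - (exp(-12L) - exp(-27L))/(15L)] = 60 × [1 - (0.630 - 0.354)/0.578] = 31.

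Under the rule this falls to about 28 at q = 10% and 23.5 at q = 25%.

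**Step 3: size if it is study drug.** The comparison is now with following entrants to their first non-study therapy. Simulated HRs, with an assumed HR of 0.50 for any next therapy, placebo median 18 months and q = 25%:

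| Assumed median open-label duration | Follow to first non-study therapy | SAP rule |
|---|---|---|
| 6 months | 0.58 | 0.67 |
| 12 months | 0.62 | 0.67 |
| 18 months | 0.65 | 0.67 |
| 24 months | 0.67 | 0.67 |

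Across assumed placebo medians of 12 to 24 months and open-label medians of 6 to 12 months, following entrants gives 0.53 to 0.55 at q = 10% (rule: 0.56) and 0.57 to 0.65 at q = 25% (rule: 0.67). With a placebo median of 12 months and open-label medians of 18 to 24 months the order reverses: 0.68 to 0.69 against 0.66 to 0.67.

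The HRs, medians, open-label durations and q in Steps 2 and 3 are assumptions.

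**The case against.** The strongest defence is that the rule is a consistent convention. SAP 7.4 restricts efficacy analysis to the double-blind period unless otherwise specified, and the other time-to-event endpoints are also censored at or before open-label entry. If open-label enzalutamide is study drug, as most passages suggest, the HR is a coherent double-blind-period quantity, and following patients further is a different estimand. In addition, the endpoint is descriptive. Open-label entrants already count as progression events in rPFS and TTPP_3, and SAP Appendix 3 reports how many switch.

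Most of this stands. It supports keeping the rule as the main analysis and treating the matter as minor. It does not remove the problem: the endpoint is built on therapies started after the last dose of study drug, so a double-blind-only cut sits awkwardly with it, and the cut falls on one arm, after progression. The related outputs give no time-to-next-therapy HR that follows the switchers.

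A reader might infer that the HR is simply biased against enzalutamide by 1/(1-q). The documents do not support that. The factor is an identity under the less supported reading, and q is not given. A reader might also infer that open-label entry should be the event in the main analysis. That is debatable, because the free switch before unblinding is offered to placebo patients only.

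**Conclusion.** The point holds in a limited form. Before study-wide unblinding, the censoring in SAP 6.1.2.5 is one-sided and informative for a descriptive secondary HR. On the better-supported study-drug reading, direction and size depend on open-label duration: in the settings tried the gap was at most about 0.10 in HR at q = 25% and 0.03 at q = 10%, shrank with longer open-label treatment and could reverse. On the next-therapy reading the HR moves towards 1, and past it if q is large: 0.50 becomes 0.56 or 0.67 at assumed q of 10% or 25%. The constant-q factor would be only approximate if q changed strongly over time.

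The rule does not enter the primary TTPP test, its alpha or its power. Severity is minor; this is a cheap improvement.

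**What to change.** 1. Keep the current rule as the main analysis.
2. State in SAP 6.1.2.5 whether open-label enzalutamide is study drug or a new antineoplastic therapy, and use the same definition in SAP 7.2.4.
3. Report the number of patients censored at open-label entry, by arm.
4. Pre-specify two supplementary analyses for entries before study-wide unblinding: (a) follow entrants to their first non-study antineoplastic therapy, using the open-label long-term follow-up; (b) count the first open-label dose as an event. Entries after study-wide unblinding may stay censored.

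The cost is a few sentences and minor programming. The open-label start dates are already needed for other censoring rules, and the follow-up data are already collected. SAP section 1 allows version-controlled revision before hard lock. SAP version 1.0 (21 December 2022) also predates Protocol version 5.0 (6 January 2023), so its placebo-only description of the open-label phase needs aligning anyway.

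The downside is that analysis (b) may favour enzalutamide, because an easy switch for placebo patients alone can bring their events forward. In simulation with an assumed HR of 0.50, placebo median 18 months and q of 10% to 25%, entry 1 month early gives 0.49 to 0.50 and entry 3 months early gives 0.48 to 0.49. Read (b) as a sensitivity bound beside the main result.
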